a Screening/Baseline assessments may be performed during several clinic visits. If the final Day 90 visit in the ALN-TTRSC-002 study is within 28 days of the first dose administered in this study, then visit procedures performed as part of the Day 90 visit do not need to be repeated at the Screening/Baseline visit. If the Day 90 visit in the ALN-TTRSC-002 study occurred within 90 days of the first dose administered in this study, the echocardiogram and CMR do not need to be repeated at the Screening/Baseline visit.

- b The results from samples collected predose are not needed prior to dosing.
- c The 14-day window applies to study assessments. Dosing is to maintain the weekly schedule ( $\pm$  2 days).
- d Refer to [Table 2](#) for the continued Schedule of Assessments in Years 3 and 4 and for the End-of-study or Early Termination (ET) visit. For patients who discontinue early and provide consent, overall health status will be documented by either telephone contact or non-patient contact follow-up (eg, medical record check) at time points corresponding to study Day 504 (Week 72), if applicable, and study Day 1344 (Week 192).
- e Prior to Screening/Baseline activities, the patient will sign and date an ICF. No study procedures should be performed prior to informed consent being obtained.
- f During the treatment period, doses will be administered weekly ( $\pm$  2 days). Doses may be administered and some assessments may be performed at the clinical site or at home according to Section 5.5.
- g Subcutaneous injection of ALN-TTRSC into the abdomen on Day 0 (after completion of all pre-dose evaluations and procedures) and then on subsequent days into other quadrants of the abdomen. The upper arm or thigh may also be used (see the ALN-TTRSC Pharmacy Manual). Dosing on Days 1, 2, 3, and 4 must be performed approximately 24  $\pm$  4 hours after the preceding dose of study drug.
- h On Day 0 pre-dose, only interval medical history will be collected. Changes in medical history during the treatment period will be captured as TEAEs or concomitant medication(s) as appropriate.
- i Serology tests include HBsAb, HBsAg, and anti-HCV Ab.
- j Assessment should be performed before dosing.
- k The pregnancy test will be performed for WOCBP only. A serum pregnancy test should be performed at Screening/Baseline. Urine pregnancy tests at other visits.

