b The End-of-study or ET visit is scheduled approximately 7 days following the last dose. The Follow-up visit is scheduled approximately 4 weeks following the End-of-study or ET visit, if applicable. Patients who discontinue early will be required to report to the clinic for an End of Study visit and a Follow-up visit. For patients who discontinue

early and have provided consent, overall health status will be documented by either telephone contact or non-patient contact follow-up (eg, medical record check) at time points corresponding to study Day 504 (Week 72), if applicable, and study Day 1344 (Week 192).

- c During the treatment period, doses will be administered weekly ( $\pm$  2 days). Doses may be administered at the clinical site or at home according to Section 5.5.
- d Subcutaneous injection of ALN-TTRSC into the abdomen. The upper arm or thigh may also be used (see the ALN-TTRSC Pharmacy Manual).
- e Assessment should be performed before dosing.
- f The pregnancy test will be performed for WOCBP only. A serum pregnancy test should be performed at Screening/Baseline. Urine pregnancy tests at other visits.
- g The serum creatinine values should be in mg/dL to 2 decimal places (e.g., 0.95 mg/dL) OR values in  $\mu$ mol/L to the nearest whole number (e.g., 84  $\mu$ mol/L) when calculating eGFR using the MDRD study equation; see <http://nkdep.nih.gov/lab-evaluation/gfr-calculators.shtml> for an eGFR calculator.
- h Vital sign measurements include blood pressure, pulse rate, oral body temperature, and respiratory rate. Vital signs will be measured manually in the supine position after the patient has rested comfortably for 10 minutes. Each patient's blood pressure should be taken using the same arm. Vital signs should be collected during any unscheduled clinic visit.
- i For the 12-Lead ECG, each lead shall be recorded for at least 3 beats at a speed of 25 mm/s. Triplicate recordings will be obtained. The electrophysiologic parameters assessed will be rhythm, ventricular rate, PR interval, QRS duration, QT interval, ST and T-waves and QTcB.
- j Coagulation studies include PT, aPTT, and INR and will be performed on all patients.
- k Blood samples for vitamin A will be analyzed by a central laboratory.
- l Refer to Table 4 for PK Sampling Schedule.

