#### **4.4.2. Handling of Withdrawals**

In the event a patient withdraws or is withdrawn from the study, the Investigator will inform the Medical Monitor at the clinical research organization (CRO) and Alnylam immediately. If there is a medical reason for withdrawal, the patient will remain under the supervision of the Investigator for protocol-specified safety follow up procedures.

When a patient withdraws or is withdrawn from the study, every effort should be made to conduct a complete ET visit as soon as possible following the patient's withdrawal, as described in Table 2.

If a patient is withdrawn for an AE, appropriate medical care should be provided and, if possible, the AE should be followed until resolution.

A patient who fails to return for final evaluations will be contacted by the site in an attempt to have the patient comply with the protocol. The site will follow up by telephone at least twice and send a registered letter to any patient who fails to return for the final evaluation.

When a patient withdraws from the study, the primary reason for discontinuation must be recorded in the appropriate section of the case report form (CRF) and all efforts will be made to complete and report the observations as thoroughly as possible.

For patients who discontinue early and have provided consent, overall health status will be documented by telephone contact or non-patient contact follow-up (eg, medical record check) at the scheduled time points.

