#### **6.4.9. Adverse Events**

Adverse events will be collected beginning with the first dose of study drug and through the Follow-up visit. After Day 84, the site should contact the patient by phone at least monthly to collect information on adverse events between clinic visits. See Section 7 for more details on the collection and reporting of AEs.

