### 7.2. Serious Adverse Event Definition

An SAE is any untoward medical occurrence that at any dose:

- Results in death;
- Is life-threatening (an event which places the patient at immediate risk of death from the event as it occurred. It does not include an event that had it occurred in a more severe form might have caused death);
- Requires inpatient hospitalization or prolongation of existing hospitalization;
- Results in persistent or significant disability/incapacity;
- Is a congenital anomaly or birth defect;
- An important medical event that may not be immediately life-threatening or result in death or hospitalization but may jeopardize the patient and may require intervention to prevent one of the other outcomes listed above. Examples of such events include allergic bronchospasm requiring intensive treatment in an emergency room or at home, blood dyscrasias, convulsions, or the development of drug dependency or abuse.

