### 7.3. Eliciting Adverse Event Information

The patient should be asked about medically relevant changes in his/her health since the last visit. The patient should also be asked if he/she has been hospitalized, had any accidents, used any new medications, or changed concomitant medication routines (both

prescription and OTC). Between clinic visits, the Investigator or designated study site staff should contact the patient by telephone on at least a monthly basis to collect additional information about any medically relevant health changes that may have occurred since the study visit. The patient should also be instructed to contact the study site to report any changes in health status.

In addition to patient observations, AEs will be documented from any clinically relevant laboratory findings, physical examination findings, ECG changes, or other findings that are relevant to patient safety.

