#### **7.4. Adverse Event Reporting**

The Investigator is responsible for reporting all AEs that are observed or reported after the first dose of study drug through the Follow-up visit regardless of their relationship to study drug or clinical significance.

Any medical condition that is present when a patient is screened and does not deteriorate is captured as medical history and should not be reported as an AE. However, if it does deteriorate at any time during the study, it should be reported as an AE.

All AEs that occur after the first dose of study drug must be reported in detail on the appropriate CRF page and recorded in the site's source records. The description of the AE will include the onset time and date, duration, severity, seriousness (see Section 7.8) relationship to study drug, action taken, and outcome (including time and date of resolution, if applicable). Adverse events resulting from concurrent illnesses, concomitant medications, or progression of disease states must also be reported. The Medical Dictionary for Regulatory Activities (MedDRA®) will be used to code AEs.

For AEs that are considered AEs of clinical interest, additional clinical information may be collected based upon the severity or nature of the event.

If a patient has ISRs meeting any of the following criteria, the Investigator, or designee, should contact the Medical Monitor and submit a supplemental ISR eCRF:

- ISRs that are recurrent and/or demonstrate a pattern of increasing severity
- Any ISR that is determined to be severe and/or a cause for study drug discontinuation
- Any ISR which, in the opinion of the Investigator, requires further medical evaluation or treatment

In some cases, where it is medically appropriate, further evaluation may include photographs, referral to a dermatologist, skin biopsy, or other laboratory testing. If a biopsy was obtained, the Sponsor may request that the biopsy also be reviewed by a central dermatopathologist. To better understand the safety profile of the study drug, additional analysis of biopsy tissue may be performed as allowed by local regulations.

For patients with hepatic AEs, additional information, including, clinical history, course of event, and local laboratory results to monitor LFT levels or other laboratory parameters, may be collected.

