### **9.2.4. Informed Consent Form**

Written informed consent in compliance with ICH and local regulations will be obtained from each patient prior to undergoing any protocol-specific tests or procedures that are not part of routine care.

Alnylam will provide an ICF template to the Investigator for use in developing a site-specific ICF. Prior to submission of the site-specific ICF to the IEC/IRB, the site-specific ICF must be reviewed and approved by Alnylam. Any changes requested by the IEC/IRB must also be approved by Alnylam. The final IEC/IRB approved ICF must be provided to Alnylam. Revisions to the ICF required during the study must be approved by Alnylam, and a copy of the revised ICF provided to Alnylam.

Before recruitment and enrollment, each prospective patient will be given a full explanation of the study and be allowed to read the ICF. Once the Investigator is assured that the patient understands the commitments of participating in the study, the patient will be asked to sign and date the ICF. A copy of the fully signed and dated ICF will be given to the patient. The original will be maintained in the patient's medical record at the site. All active patients will sign an updated ICF if revisions are made to the ICF during the course of the study.

For patients who discontinue early and have provided consent, overall health status will be documented by telephone contact or non-patient contact follow-up (eg, medical record check) at the scheduled time points in an attempt to minimize the extent of missing data.

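### Do the unspecified health-status checks after early discontinuation leave the mortality and hospitalization outcomes without the data they need?

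*Protocol*

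**What the plan says.** Section 2.2 makes mortality and hospitalization secondary objectives. Section 8.2.4 plans Kaplan-Meier curves for all-cause and cardiovascular death, and frequencies of all, cardiovascular and heart-failure admissions. Section 8.2.9 right-censors patients with no recorded death.

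During the study these events arrive as serious adverse events. Section 7.2 counts among its criteria death and any event that "Requires inpatient hospitalization or prolongation of existing hospitalization". Section 7.3 adds a direct question at visits: "The patient should also be asked if he/she has been hospitalized". Telephone contact between visits is at least monthly.

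The reporting window is stated twice. Section 6.4.9: "Adverse events will be collected beginning with the first dose of study drug and through the Follow-up visit". Section 7.4 makes the investigator responsible for events observed or reported "after the first dose of study drug through the Follow-up visit regardless of their relationship to study drug".

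After early discontinuation, Table 2 footnote b covers patients who stop "early and have provided consent, overall health status will be documented by either telephone contact or non-patient contact follow-up (eg, medical record check", at times corresponding to Day 504, if applicable, and Day 1344. Table 1 footnote d says the same in nearly the same words: "For patients who discontinue early and provide consent, overall health status will be documented by either telephone contact". Section 4.4.2 ("overall health status will be documented by telephone contact or non-patient contact follow-up (eg, medical record check) at the scheduled time points") and section 9.2.4 omit the days. Section 9.2.4 gives the purpose: the checks are made "at the scheduled time points in an attempt to minimize the extent of missing data".

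**The concern.** A Kaplan-Meier curve needs a date for every death, and the cardiovascular curve also needs a cause. The hospitalization summaries need admissions with a reason. The protocol does not say that the post-discontinuation checks record any of these; it names only overall health status, which it does not define.

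If a check established only that a patient had died, the death would have no date for one curve and no cause for the other. If a death went unrecorded, the patient would be censored. Patients who leave because they are getting worse would then drop out of the risk set shortly before dying, and the curve would look too favorable. With about 25 patients, one death is 1/25 = 4 points of crude survival, so a few lost deaths would be visible. An analysis plan can set censoring rules, but it cannot recover a date or cause that nobody asked for.

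**Working it through.** **Inputs.** Last planned dose Day 1337 (section 3.1). End-of-study or early-termination visit about 7 days after the last dose, and Follow-up visit about 4 weeks later (Table 2 footnote b). Checks at Days 504 and 1344. About 25 patients (section 8.1).

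**Reproducing the schedule.** 1337 + 7 = 1344, and 1344 + 28 = 1372, the Follow-up day in Table 2. From last dose to Follow-up is 1372 − 1337 = 35 days, or 21 to 49 days with the ±14-day window.

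**Time after new-event collection ends.** For last dose on day D, this is 1344 − (D + 35):

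| Last dose | Follow-up | Days to 1344 | Share of 1344 | Intervals between contacts (days) |
|---|---|---|---|---|
| 84 | 119 | 1225 | 91% | 385, then 840 |
| 168 | 203 | 1141 | 85% | 301, then 840 |
| 336 | 371 | 973 | 72% | 133, then 840 |
| 672 | 707 | 637 | 47% | 637 |
| 1008 | 1043 | 301 | 22% | 301 |

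The longest interval between contacts is 1344 − 504 = 840 days (2.3 years). From D = 469 the Follow-up visit falls at or after Day 504 (469 + 35 = 504), so only the Day 1344 check remains. These are lengths of calendar time. They do not measure lost information, because the planned checks fall within or at the end of each interval and can look back over it.

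**Could deaths fall there?** Yes. Section 1.1.2 gives median survival after diagnosis of 2.5 to 3.5 years. Under an assumed exponential curve, a patient alive on Day 371 dies before Day 1344 with probability 1 − 0.5^(973/365.25/median): 52% for a median of 2.5 years and 41% for 3.5. Enrolled patients are already past diagnosis, so this is only a rough guide.

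**Bias if those deaths were never recorded.** Suppose m of 25 patients leave before any death and are all censored. The Kaplan-Meier estimate then exceeds full-follow-up survival by (m/25) × (survival of stayers − survival of leavers). With assumed m = 3 to 8 and an assumed difference of 0.20 to 0.40, the excess runs from (3/25) × 0.20 = 2.4 points to (8/25) × 0.40 = 12.8 points. It is zero if leavers do no worse. As an example, take 20 stayers with 8 deaths and 5 leavers censored early. The Kaplan-Meier estimate is 12/20 = 60%. With the leavers followed, survival is 15/25 = 60% if 2 of them die and 12/25 = 48% if all 5 do.

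**What the protocol provides against this.**
- The two checks may be made from medical records, and section 9.2.4 ties them to limiting missing data.
- Section 7.5 follows serious events until they are resolved, chronic or stable, with no 35-day limit. Section 7.8 repeats this whatever the relationship to study drug, and allows discharge summaries and autopsy reports to be requested.
- Section 4.4.2 keeps patients withdrawn for a medical reason under the investigator's supervision for the protocol's safety follow-up, and asks that an adverse event leading to withdrawal be followed to resolution if possible.

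So the Follow-up visit ends the collection of new events, not the follow-up of serious events already open. The 2.4 to 12.8 points apply only if the checks fail to record deaths, which nothing in the protocol says.

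**The case for a change.** The strongest case for a change is that this is data collection and belongs in the protocol. Three of the planned summaries depend on cause (cardiovascular death, cardiovascular admission, heart-failure admission). A telephone call that asks generally about health could miss an admission two years back or return a death without its cause. The continued follow-up of serious events stops once the patient is judged chronic or stable, so it does not cover a later, new event. The remedy would be cheap: one sentence in four places, with no added contact.

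Much of this stands. The term is undefined, the protection for open serious events is partial, and recall over 840 days is imperfect. Patients who do not consent stay uncovered under any wording. What does not stand is the step from items not named to items not recorded. Case report form pages and study manuals ordinarily hold a check's field list, and neither is shown here. In a study with mortality and hospitalization among its named outcomes, staff opening a medical record to limit missing data would look for death, its date and cause, and admissions. Right-censoring patients with no recorded death is ordinary Kaplan-Meier practice. How admissions are expressed per unit of follow-up is a matter for the analysis plan.

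**Conclusion.** No change is called for. The date arithmetic is right: new-event collection ends about 35 days after the last dose, and later contacts can be 840 days apart. The gap concerns the content of checks that already exist and already have the right purpose, and a sensible case report form fills it. Harm needs a further assumption, that a check finds a death and leaves it undated or unclassified, or misses it altogether; the protocol neither says nor implies this. Without dropout and survival figures for leavers, the bias cannot be sized from the document and may be zero.

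The stakes are also limited. This is a single-arm, open-label extension with mainly descriptive analyses and safety as its primary objective. The secondary clinical objective concerns long-term dosing, on which deaths long after the last dose bear only indirectly. The conclusion assumes that the forms for the Day 504 and Day 1344 checks ask for vital status, date and cause of death, and admissions since last contact. Whoever holds the forms can confirm that without amending the protocol.

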**Table 3: Schedule of Assessments for Weekly Dosing Days between Clinic Visits**

Study Day (+14 Days):	Study Drug Administration a,b	Concomitant Medication, AEs, and Vital Signs c,d	TTR Sample e	Serum Chemistry and Hematology
Year 1				
Clinic Visit (Wk 1, Day 7) - See Table 1				
14	X	X	X	X
21,35,42,49,63,70,77	X	X		
28,56	X	X	X	X
Clinic Visit (Wk 12, Day 84) - See Table 1				
91,98,105,119,126,133,147,154,161	X			
112,140	X	X		
Clinic Visit (Wk 24, Day 168) - See Table 1				
175,182,189,203,210,217,231,238,245	X			
196,224	X	X		
Clinic Visit (Wk 36, Day 252) - See Table 1				
259,266,273,287,294,301,315,322,329	X			
280,308	X	X		
Clinic Visit (Wk 48, Day 336) - See Table 1				
343,350,357,371,378,385,399,406,413	X			
364,392	X	X		
Year 2				
Clinic Visit (Wk 60, Day 420) - See Table 1				
427,434,441,455,462,469,483,490,497	X			
448,476	X	X		
Clinic Visit (Wk 72, Day 504) - See Table 1				
511,518,525,539,546,553,567,574,581	X			
532,560	X	X		
Clinic Visit (Wk 84, Day 588) - See Table 1				
595,602,609,623,630,637,651,658,665	X			
616,644	X	X		
Clinic Visit (Wk 96, Day 672) - See Table 2				
679, 686, 693, 707, 714, 721, 735, 742, 749	X			
700,728	X	X		
Year 3				

**Table 3: Schedule of Assessments for Weekly Dosing Days between Clinic Visits**

Study Day (+14 Days):	Study Drug Administration a,b	Concomitant Medication, AEs, and Vital Signs c,d	TTR Sample e	Serum Chemistry and Hematology
Clinic Visit (Wk 108, Day 756) - See Table 2				
763,770,777,791,798,805,819,826,833	X			
784,812	X	X		
Clinic Visit (Wk 120, Day 840) - See Table 2				
847,854,861,875,882,889,903,910,917	X			
868,896	X	X		
Clinic Visit (Wk 132, Day 924) - See Table 2				
931,938,945,959,966,973,987,994,1001	X			
952,980	X	X		
Clinic Visit (Wk 144, Day 1008) - See Table 2				
1015,1022,1029,1043,1050,1057,1071,1078,1085	X			
1036,1064	X	X		
Year 4				
Clinic Visit (Wk 156, Day 1092) - See Table 2				
1099,1106,1113,1127,1134,1141,1155,1162, 1169	X			
1120,1148	X	X		
Clinic Visit (Wk 168, Day 1176) - See Table 2				
1183,1190,1197,1211,1218,1225,1239,1246, 1253	X			
1204,1232	X	X		
Clinic Visit (Wk 180, Day 1260) - See Table 2				
1267,1274,1281,1295,1302,1309,1323, 1330,1337	X			
1288,1316	X	X		

Abbreviations: AE = adverse event, TTR = transthyretin

- a During the treatment period, doses will be administered weekly ( $\pm$  2 days). Doses may be administered at the clinical site or at home according to Section 5.5.
- b Subcutaneous injection of ALN-TTRSC into the abdomen on Day 0 and then on subsequent days into other quadrants of the abdomen. The upper arm or thigh may also be used (see the ALN-TTRSC Pharmacy Manual).
- c Adverse events and concomitant medications information may be collected by the site via phone on a monthly basis or by a home healthcare professional.
- d Vital sign measurements include blood pressure, pulse rate, oral body temperature, and respiratory rate. Vital signs will be measured manually in the supine position after the patient has rested comfortably for 10 minutes. Each patient's blood pressure should be taken using the same arm. Vital signs should be collected prior to each weekly dose, up to Day 84.

e TTR samples should be taken pre-dose.

